An Open-Label Study of the Apollo Device for Fatigue in Systemic Sclerosis

Test device: Apollo

Study purpose: Evaluate the efficacy and use patterns of Apollo

Clinical study phase: II

Version no: 1

Version Date February 1, 2021

Sponsor Investigator:

The study will be conducted in compliance with the protocol, ICH-GCP and any applicable regulatory requirements.

Confidential

The information provided in this document is strictly confidential and is intended solely for the guidance of the clinical investigation. Reproduction or disclosure of this document - whether in part or in full - to parties not associated with the clinical investigation, or its use for any other purpose, without the prior written consent of the sponsor is not permitted.

Throughout this document, symbols indicating proprietary names (®, TM) may not be displayed. Hence, the appearance of product names without these symbols does not imply that these names are not protected.

Synopsis

Title	An Open-Label Study of the Apollo Device for Fatigue in Systemic Sclerosis
Short title	The Apollo in Systemic Sclerosis
Clinical study phase	II
Study objective(s)	The primary objective of this study is to provide preliminary data on the tolerability and efficacy of the Apollo system for the management of fatigue in systemic sclerosis.
Test device	Apollo System
Mechanism of use	The Apollo system consists of a wearable device whose frequency of use is controlled by the participant. The participant will install the study mobile application on a mobile device of their choosing. The wearable device is controlled by the mobile app through which the participant can choose when and for how long to use it.
Location of use	Wrist or ankle
Duration of use	4 weeks
Background treatment	Patients will continue any existing prescription medication, including prednisone and immunosuppressives, at steady doses for 4 weeks prior to baseline (visit 1) and during the four-week intervention period.
Indication	Scleroderma-associated fatigue
Diagnosis and main criteria for inclusion	
 ▪ Men or women aged 18 years and older, inclusive ▪ Systemic Sclerosis as defined by 2013 the American College of Rheumatology (ACR) / European League Against Rheumatism (EULAR) classification. ▪ Steady daily doses of any immunosuppressive medication, vasodilators, antidepressants and anxiolytic use for 4 weeks prior to baseline. ▪ PROMIS-fatigue score of at least 45 ▪ Currently owns and operates a smart phone regularly ▪ Ability to provide informed consent
Study Design	Open label, single-arm, single center US study
Type of control	None
Number of participants	30
Primary outcome variable	Change in the PROMIS-Fatigue scale at four weeks

30

Plan for statistical analysis

The planned sample size of 30 SSc participants is based on practical considerations to obtain estimates of the magnitude of treatment differences for efficacy and safety rather than a desired power for a pre-specified difference.

From similar studies on Rheumatoid Arthritis and Systemic Lupus Erythematosus, the improvement of T-score after treatment is about 5. The standard deviation for general population is 10. However, we are restricting our population to participants with fatigue T-scores of less than 54 (with low score indicating high fatigue). With the range of T-score reduced about half, we expect the standard deviation to be about 5. The effect size is expected to be 1 (5/5).

Using paired t-test, we have 86% power to detect the effect size of 1 when we recruit 30 patients at a significance level of 0.05. We asked the IRB for the option of increasing the number of patients to 40, which will give us about 81% power to detect a smaller effect size of 0.8 at a significance level of 0.05.

Descriptive statistics will be derived for all clinical variables, mean and standard deviation for continuous outcomes and percentages for categorical and dichotomous variables.

The primary outcome of interest is fatigue, as measured by the FACIT-Fatigue. We will compare the mean change from baseline and four weeks in a repeated measures model.

The p-values resulting from formal statistical tests will be interpreted from a hypothesis-generating, rather than a confirmatory framework.

Table of contents

1. Introduction	9
1.1 Background	9
1.1.1 Scleroderma (systemic sclerosis).....	9

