4.1.1 Screening phase (up to 4 weeks prior to baseline visit)

After providing written informed consent, participants will undergo a screening evaluation to determine their eligibility (see Section [7.1](#) for a detailed schedule of events). Participants will complete the PROMIS-Fatigue scale to determine if they have moderate to severe fatigue. If a T score of 45 is obtained, and all inclusion criteria are met, then the patient may proceed to the observation phase. Participants will be given the 7-day diary to be completed starting one week prior to their scheduled baseline visit. They will be reminded by telephone call or text (based on

their preference) to begin their diary collection.

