5.1 Eligibility

5.1.1 Inclusion criteria

Participants must meet the following criteria to be eligible for enrollment in the study:

1. Signed written informed consent
2. Men or women aged 18 years and older
3. Diagnosis of Systemic sclerosis, as defined by 2013 American College of Rheumatology/ European Union League Against Rheumatism classification of SSc.
4. Baseline T score of 45 on the PROMIS-Fatigue scale.
5. Steady daily doses and any immunosuppressive medication, vasodilators, antidepressants and anxiolytic use for 4 weeks prior to baseline.
6. Currently owns and operates an iOS or Android smart phone regularly
7. Ability to comply with the clinical visits schedule and the study-related procedures.
8. Subjects who have struggled with symptoms of SSc (specifically fatigue and Raynauds) who have not received adequate symptom relief from prior treatment attempts (treatment-resistant) will be prioritized.
- 9.

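### The sample size assumes fatigue T-scores below 54 with low scores meaning more fatigue, but the entry rule is a floor of 45 with no upper limit

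*Combined protocol and SAP*

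**What the plan says.** **Entry rule.** The synopsis (main inclusion criteria) requires a "PROMIS-fatigue score of at least 45". Section 4.1.1 lets a patient proceed "If a T score of 45 is obtained, and all inclusion criteria are met", with no inequality, at screening. Section 5.1.1, item 4, reads "Baseline T score of 45 on the PROMIS-Fatigue scale", again with no inequality, but at baseline. Section 4.1.1 gives the purpose: "Participants will complete the PROMIS-Fatigue scale to determine if they have moderate to severe fatigue".

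**Planning population.** The synopsis (Plan for statistical analysis) says "we are restricting our population to participants with fatigue T-scores of less than 54 (with low score indicating high fatigue". It then argues "With the range of T-score reduced about half, we expect the standard deviation to be about 5". From similar studies in other rheumatic diseases it takes that "the improvement of T-score after treatment is about 5", and so reaches an effect size of 5/5 = 1.

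**Instrument and direction.** The same synopsis section states "The primary outcome of interest is fatigue, as measured by the FACIT-Fatigue". The synopsis outcome row and Sections 2, 7.3 and 8.2.2 all name PROMIS-Fatigue. None of these says whether a rise or a fall in score is improvement.

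**The concern.** The planning paragraph describes a restriction that the trial does not apply. A limit of 54 is absent from the synopsis criteria, Section 4.1.1, the inclusion list (5.1.1) and the exclusion list (5.1.2). The SD was halved from 10 to 5 on the strength of that limit alone.

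The scoring direction is the more serious part. If low scores mean high fatigue, a floor of 45 removes the most fatigued patients and leaves the least fatigued unrestricted. If high scores mean high fatigue, the floor does its job and the planning sentence is wrong. Both cannot stand. The same ambiguity reaches the primary endpoint. The two-sided p-value is the same either way, but its meaning as benefit or harm is not. Because the planning section names a different instrument from the rest of the protocol, a reader cannot tell which scale the 54 or the stated direction belongs to.

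**Working it through.** **1. The plan's own figures.** Effect size 5/5 = 1 reproduces. The stated 86% power for a paired t-test with 30 patients does not: the exact two-sided calculation at 0.05 gives 99.96%. The 86% matches a one-sided, two-sample comparison of 15 per arm (86.3% by z). That is a separate error and is not used below.

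**2. The passages side by side.**

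| Place | Limit | Direction |
|---|---|---|
| Synopsis, inclusion | 45 or above | not stated |
| 4.1.1 (screening) | 45, no inequality | not stated; aim is to find fatigued patients |
| 5.1.1, item 4 (baseline) | 45, no inequality | not stated |
| Synopsis, sample size | below 54 | low = more fatigue |

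Scores of 45 to 53 satisfy both limits, so the eligible set is not empty. The conflict is that one limit is never applied and that the stated direction defeats the other.

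**3. The SD under each limit.** Inputs: population SD 10 (synopsis). The documents give no mean, so I assume normality and means of 40 to 60.

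- Floor at 45: a = (45 − mean)/10, λ = φ(a)/[1 − Φ(a)], SD = 10√(1 + aλ − λ²).
- Ceiling at 54: b = (54 − mean)/10, κ = φ(b)/Φ(b), SD = 10√(1 − bκ − κ²).

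Example at mean 50:
- Floor: a = −0.5, λ = 0.509, SD = 10√(1 − 0.255 − 0.259) = 6.97.
- Ceiling: b = 0.4, κ = 0.562, SD = 10√(1 − 0.225 − 0.316) = 6.78.

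Power is the exact two-sided paired t-test with n = 30, alpha 0.05 and noncentrality (5/SD)√30. Like the plan, it uses the SD of scores as if it were the SD of change.

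| Assumed mean | SD, below 54 | SD, 45 or above | 5/SD, 45 or above | Power, below 54 | Power, 45 or above | Share of those at 45 or above who are also below 54 |
|---|---|---|---|---|---|---|
| 40 | 8.63 | 5.18 | 0.96 | 87% | >99% | 74% |
| 45 | 7.75 | 6.03 | 0.83 | 93% | 99% | 63% |
| 50 | 6.78 | 6.97 | 0.72 | 97% | 97% | 50% |
| 55 | 5.85 | 7.94 | 0.63 | 99% | 92% | 36% |
| 60 | 5.03 | 8.79 | 0.57 | >99% | 85% | 22% |

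With the unrestricted SD of 10 the effect size is 0.5 and the power 75%.

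**4. Reading the table.** Across these means, an SD of 5 appears only at the edge: 5.03 under the ceiling at mean 60, and not quite (5.18) under the floor at mean 40. Halving the distribution does not halve the SD. At mean 45 the floor removes exactly half, and the SD is 10√(1 − 2/π) = 6.03.

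**The case against.** The strongest reply is that little turns on the faulty sentence. The synopsis and Section 8.5 say that 30 patients were chosen on practical grounds, and Section 8.1 makes p-values hypothesis-generating and the analysis largely descriptive. Power is not the problem, and the p-value does not change. That stands as far as sample size goes. It does not cover who is enrolled or how the primary result is read, which matter at least as much in a pilot whose product is an estimate.

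Second, the entry rule can be read sensibly: a floor of 45, abbreviated in 4.1.1 and 5.1.1, with high scores meaning more fatigue. On that reading only the planning sentence is out of line. This may be what was meant, but it requires the reader to overrule the only direction the protocol states. The scoring might be given in Appendix 10.1, which is listed but not reproduced, or in the separate SAP promised in Section 8.1. Neither would remove the contradictory sentence. The mismatch of visits is partly covered, since PROMIS-Fatigue is collected at both visits, eligibility is reconfirmed at baseline (7.1.2.2), and the two visits may be combined (4.1). On its own it would be a minor point.

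Third, a paired t-test needs the SD of change, which a limit on baseline scores does not determine. With equal variances, SD of change = SD√(2(1 − ρ)). A correlation of 0.74 would bring 6.97 back to 5, and 0.80 would do so for 7.94. The answer also depends on the means considered: at mean 35 the floor gives SD 4.5, and at mean 65 the ceiling gives 4.3. If both limits applied, the SD would be about 2.5 and the effect size about 2. All of this is correct. It means the effect-size range shows what the plan's reasoning yields for the eligible group and is not an estimate of the true value. It also means the plan's figure of 1 has no support in the documents.

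**Conclusion.** The contradiction is real and needs correcting. The restriction behind the SD of 5 and the effect size of 1 is not an entry criterion, and the only stated scoring direction runs against both the floor of 45 and its stated purpose. Following the plan's own reasoning for patients at 45 or above, the effect size for a 5-point change is 0.96 down to 0.57. This assumes normal scores, SD 10, a mean between 40 and 60, and the SD of scores standing in for the SD of change. Power at 30 patients remains at least 85% under those assumptions, so the sample size is not shown to be inadequate. The consequence lies in the definition of the population and in the sign of the primary result. The priority given in inclusion item 8 to patients with inadequately relieved symptoms sets no threshold and does not settle the matter.

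**What to change.** Reconcile the synopsis with Sections 4.1.1 and 5.1.1:

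- Name one fatigue instrument throughout and state its scoring direction once.
- Use the same inequality, at the same named visit, in the synopsis, 4.1.1 and 5.1.1. The cut-off is for the sponsor to choose, but it must agree with the stated direction and with the severity of fatigue that 4.1.1 sets out to select.
- Replace the planning sentence about scores below 54. Restate the SD of change and the effect size for the population actually eligible, and give their source.
- State in 7.3 and 8.2.2 which sign of change is improvement.

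This is a wording amendment and needs no new data collection. The one drawback is that the restated effect size may be less favourable than 1.

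### The synopsis obtains an SD of 5 and an effect size of 1 by halving the population SD, which does not follow from the entry cut and is not the SD of change that a paired test needs

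*Combined protocol and SAP*

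**What the plan says.** All the planning figures are in the synopsis, under the plan for statistical analysis. It cites similar studies in two other rheumatic diseases, where "the improvement of T-score after treatment is about 5". It adds that "The standard deviation for general population is 10" and that "we are restricting our population to participants with fatigue T-scores of less than 54 (with low score indicating high fatigue". From this it concludes: "With the range of T-score reduced about half, we expect the standard deviation to be about 5". The next sentence reads "The effect size is expected to be 1 (5/5", and power follows: "Using paired t-test, we have 86% power to detect the effect size of 1 when we recruit 30 patients at a significance level of 0.05".

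The entry rule is not the same throughout. The synopsis inclusion list requires a "PROMIS-fatigue score of at least 45". Section 5.1.1 has "Baseline T score of 45 on the PROMIS-Fatigue scale", with no direction, and Section 4.1.1 also names 45 without one.

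The primary endpoint is the change in PROMIS-Fatigue at four weeks (synopsis), and Section 8.2.2 names a repeated-measures t-test. The available text of the synopsis and of Section 8.5 gives no SD of change and no correlation between baseline and week 4. Both places say that 30 participants rests on practical grounds and not on a target power. No confidence interval width is stated anywhere.

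**The concern.** The SD of 5 is presented as the result of an argument, so the argument can be checked. It treats the SD as proportional to the range. Cutting one tail off a bell-shaped distribution removes sparse extremes and leaves the dense centre, so the SD shrinks by less than the range does.

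The argument also concerns the wrong quantity. Selection on the baseline score narrows the baseline distribution. It does not cap the week-4 score, and it does not fix the spread of within-person changes, which is what a paired test divides by.

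At stake is the only effect size this plan gives. The study's stated product is a preliminary estimate of the size of effect, so a reader may take the value of 1, and the tight interval it implies, as a planning input for a later controlled trial.

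**Working it through.** **Inputs from the documents:** improvement 5; population SD 10; entry below 54 or at least 45; 30 participants; two-sided 0.05 (Section 8.1). **Assumptions, not in the documents:** normal scores with mean 50; the same population SD of 10 at both visits; correlation r of 0.5 to 0.8; a device effect that adds no extra variance.

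**1. The plan's own figure.** 10/2 = 5 and 5/5 = 1. The division is right; the step from halved range to halved SD is what fails.

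**2. Baseline SD after a one-sided cut.** With the cut z SDs from the mean and the larger part kept, SD = 10 × √(1 − zλ − λ²), where λ = φ(z)/Φ(z).

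- Below 54: z = 0.4, λ = 0.3683/0.6554 = 0.562. SD = 10 × √(1 − 0.225 − 0.316) = 6.78. This keeps 66% of people.
- At least 45: by symmetry z = 0.5, λ = 0.3521/0.6915 = 0.509. SD = 10 × √(1 − 0.255 − 0.259) = 6.97. This keeps 69%.
- Exactly half the distribution (below 50): SD 6.03.
- An SD of 5 needs a cut near 44 when the lower side is kept, about 0.6 SD beyond the mean.

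Moving the assumed mean towards fatigue raises the result: 7.7 for mean 45 with entry below 54, and 7.9 for mean 55 with entry at 45 or above.

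**3. SD of the change when only baseline is truncated.** Var(change) = (1 − r)² × Var(baseline) + 100 × (1 − r²). For r = 0.5 and entry below 54: 0.25 × 45.95 + 75 = 86.5, so the SD is 9.30. Effect size is 5/SD. Power is from the noncentral t with 29 degrees of freedom. The half-width is 2.045 × SD/√30.

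| r | SD of change | Effect size | Power, n = 30 | 95% CI half-width |
|---|---|---|---|---|
| 0.5 | 9.3 | 0.54 | 81% | 3.5 |
| 0.6 | 8.4–8.5 | 0.59 | 88% | 3.2 |
| 0.7 | 7.4 | 0.67 | 94–95% | 2.8 |
| 0.8 | 6.2 | 0.81 | 99% | 2.3 |

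The two cuts agree to within rounding. For comparison, an SD of change of 5 gives a half-width of 2.045 × 5/√30 = 1.87. The range is therefore 2.30/1.87 = 1.23 to 3.49/1.87 = 1.87 times as wide.

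**4. When would an SD of change of 5 arise?** Under baseline-only truncation, at r of about 0.87. If the SD were about 7 at both visits, SD of change = SD × √(2(1 − r)), which equals 5 at r of about 0.73 to 0.74.

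**The case against.** Four arguments have weight.

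*An SD of 5 is attainable.* This stands. With an SD near 7 at both visits, a correlation of about 0.73 to 0.74 gives it. The figure is therefore unsupported and not shown to be false. That route does require the week-4 scores to be as restricted as the baseline scores, which an entry cut does not bring about.

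*The result depends on which side of which cut is kept.* This also stands. Keeping scores of 45 or below gives 5.18, and keeping scores above 54 gives 5.34; both are roughly 5. Neither is what the synopsis writes, so they do not rescue the sentence. They do show that the SD cannot be settled until the cut-off and scale direction agree.

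*Mean 50 and normality are the reviewer's inputs.* True. A mean on the less fatigued side lowers the SD (5.85 for mean 55 with entry below 54), but Section 1.1.2 describes patients as more fatigued than the general population, which moves it the other way.

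*Nothing rests on the figure.* Largely true for the sample size, which is set on practical grounds, with p-values treated as exploratory. It is less true for the estimate the study is meant to deliver.

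A reader might also infer that the effect size is really 0.7, from 5/7. The documents do not support that: it divides by a baseline SD, and the paired effect size depends on a correlation that the plan does not give.

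**Conclusion.** The derivation is wrong as written. On the plan's SD of 10 and either cut as the synopsis directs it, the baseline SD is about 7 under normality with mean 50, and the SD that the paired test needs is not derived at all. For correlations of 0.5 to 0.8 with only baseline truncated, the effect size is about 0.5 to 0.8, and the interval is roughly 1.2 to 1.9 times as wide as an SD of 5 would imply. The correlation range has no source in the documents, so these are illustrations and not corrected values.

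Two stronger readings should be resisted. The study is not shown to be too small: power at 30 stays at about 80 to 99% for a 5-point change. Nor does the plan overstate a precision it claims, because it claims none; the 1.9 is only what an SD of 5 would imply. Separately, the stated 86% does not follow from the plan's inputs either, since a two-sided paired t-test with 30 participants and effect size 1 has over 99.9% power. Correcting that figure would leave the SD argument unrepaired.

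**What to change.** In the synopsis, delete the range-halving sentence and the effect size of 1. State an SD of the change in PROMIS-Fatigue with its source. If there is no source, give a labelled assumption with a range, for example: baseline-only truncation and correlation 0.5 to 0.8 give an SD of change of about 6 to 9, an effect size of about 0.5 to 0.8, two-sided paired power at 30 participants of about 80 to 99%, and a 95% CI half-width of about 2.3 to 3.5 points.

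Before deriving any SD from the entry rule, reconcile the synopsis analysis text (below 54, low scores meaning more fatigue) with the synopsis inclusion list (at least 45) and with Sections 4.1.1 and 5.1.1 (45, no direction).

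The cost of the SD correction is about two sentences, plus the wording needed to align the entry rule. The SD correction itself changes no procedure and adds no participants. The price is a less favourable stated effect size.

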8.1 General considerations

This section presents a summary of the planned statistical analyses. A statistical analysis plan (SAP) will be written for the study that contains detailed descriptions of the analyses to be performed. The SAP will be finalized prior to unblinding of the data.

Continuous variables will be summarized using descriptive statistics including n, mean, median, standard deviation, range (e.g., minimum and maximum). Qualitative variables will be summarized using counts and percentages. Graphical methods will be used in this pilot study to assess the pattern of response over time for key variables and to assess the relationships among variables.

Unless otherwise specified, statistical analyses will be performed using SAS Version 9 or higher. Where appropriate, statistical tests will be conducted at the 0.05 significance level (with no adjustments for multiplicity) using two-tailed tests and p-values will be reported.

Given the rare nature of SSc and the consequent small sample size for this pilot study, the statistical power of any comparisons is limited (i.e., there is sufficient power to detect only large treatment differences). As such the analysis will be largely descriptive in nature. The p-values resulting from formal statistical tests will be interpreted from a hypothesis-generating, rather than a confirmatory framework.

Analysis sets

As this is an open-label study, all participant who have used the Apollo system wearable for at least one dose (one day) will be analyzed. The primary endpoint and all secondary outcomes will be assessed using this analysis set.

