8.5 Determination of sample size

SSc is a rare disease. The planned minimum sample size of 30 SSc participants is based on practical considerations to obtain preliminary estimates of the magnitude of treatment differences in efficacy and safety rather than a desired power for a pre-specified difference as would be necessary for a confirmatory study. However, with this proposed sample of 30 participants we can calculate the magnitude of treatment differences (riociguat – placebo) for the primary efficacy endpoint – the change from baseline to end of double-blind treatment in fatigue scales. There would be 80% power to detect an effect size (mean treatment difference divided by standard deviation) of While we expect that 30 subjects will be enough participants to see a significant treatment effect in this study population, we have written this protocol to allow for the inclusion of up to 100 subjects should 30 subjects be found to be an insufficient number for any reason.

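### The 86% and 81% power figures in the synopsis do not follow from its stated paired t-test inputs, which give over 99%; no SD of change is stated, so the trial's real power is unknown.

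*Combined protocol and SAP*

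**What the plan says.** The power statement is in the synopsis, under the plan for statistical analysis. It expects an improvement of about 5 T-score points, on the strength of similar studies in rheumatoid arthritis and lupus. It takes 10 as the general-population SD and halves it because enrolment is restricted to part of the scale: "With the range of T-score reduced about half, we expect the standard deviation to be about 5". The ratio 5/5 gives an effect size of 1. Then: "Using paired t-test, we have 86% power to detect the effect size of 1 when we recruit 30 patients", at a significance level of 0.05. For an optional increase to 40 patients, "which will give us about 81% power to detect a smaller effect size of 0.8 at a significance level of 0.05".

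Section 8.1 fixes the sidedness: "statistical tests will be conducted at the 0.05 significance level (with no adjustments for multiplicity) using two-tailed tests". The same section says that "there is sufficient power to detect only large treatment differences".

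Section 8.5 starts a second power statement, for a riociguat-versus-placebo contrast, and stops before giving the effect size: "There would be 80% power to detect an effect size (mean treatment difference divided by standard deviation) of While we expect".

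The synopsis also says that the sample size "is based on practical considerations to obtain estimates of the magnitude of treatment differences for efficacy and safety rather than a desired power", and section 8.5 says much the same.

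**The concern.** The test, sample sizes, effect sizes and significance level are all printed, so the two power figures can be checked directly. A paired t-test on 30 pairs with a true mean change of one SD of change should almost never miss, so 86% looks far too low. The same holds for 81% with 40 pairs at 0.8 SD.

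The input behind the effect size is also unclear. A paired t-test needs the SD of the within-patient change. The synopsis derives its SD from the spread of scores among those enrolled, and gives neither an SD of change nor a correlation between baseline and week 4.

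At stake is whether a reader can tell what T-score change the trial can detect. The synopsis holds the only completed power statement in the document, because the sentence in section 8.5 breaks off and concerns a comparison that this single-arm trial does not make.

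**Working it through.** **Inputs.** Synopsis: paired t-test; n = 30 with mean change 5, SD 5, effect size 1; n = 40 with effect size 0.8 (4 points if the SD is 5); alpha 0.05. Section 8.1: two-tailed. Synopsis and sections 4.1 and 6.2: single arm, so every patient contributes one pair. No dropout allowance is stated.

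**Method.** Let d = mean change / SD of change. Paired t-test power is the probability that a noncentral t variable, with n − 1 degrees of freedom and noncentrality d√n, falls outside ± the two-sided 5% critical value (2.045 for n = 30, 2.023 for n = 40).

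**Step 1: the plan's figures from its own inputs (SD of change = 5).**
- n = 30: d = 5/5 = 1, noncentrality 1 × √30 = 5.48, power 99.96% (stated 86%).
- n = 40: d = 4/5 = 0.8, noncentrality 0.8 × √40 = 5.06, power 99.85% (stated about 81%).

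Neither figure is reproduced. A one-sided test is further away (99.99% and 99.96%). If half the patients were lost (an assumption), 15 and 20 pairs would still give 94.9% and 92.4%. At these effect sizes 12 pairs pass 86% (88.3%) and 15 pairs pass 81% (82.1%).

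**Step 2: SD 5 read as the SD of scores.** In general, SD of change = √(SD₀² + SD₄² − 2r·SD₀·SD₄), where SD₀ and SD₄ are the SDs at baseline and week 4 and r is their correlation. Assume SD 5 at both visits and r = 0. Then SD of change = √(25 + 25) = 7.07, and power is 96.3% (n = 30, 5 points) and 93.7% (n = 40, 4 points). With equal SDs, any positive r raises both.

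**Step 3: what the stated figures need.** Solving for d at two-sided power 86% with n = 30 gives d = 0.574, so SD of change = 5/0.574 = 8.71. At 81% with n = 40, d = 0.460 and SD of change = 4/0.460 = 8.69. Both figures therefore point to about 8.7. That value can arise if the SD differs between visits. With SD₀ = 5, an assumed SD₄ = 10 and an assumed r = 0.5, SD of change = √(25 + 100 − 50) = 8.66, and power is 86.3% and 81.3%. The effect sizes would then be 5/8.66 = 0.58 and 4/8.66 = 0.46, not 1 and 0.8.

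**Step 4: sensitivity to the SD of change (two-sided).**

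| SD of change | Basis | n = 30, 5 points | n = 40, 4 points |
|---|---|---|---|
| 5 | effect sizes as stated | 99.96% | 99.85% |
| 7.07 | assumed SD 5 at both visits, r = 0 | 96.3% | 93.7% |
| 8.66 | assumed SD 5 then 10, r = 0.5 | 86.3% | 81.3% |
| 10 | assumed | 75.4% | 69.4% |

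**Step 5: detectable change at 80% power, two-sided.** d = 0.529 at n = 30 and 0.454 at n = 40. At n = 30 this is 0.529 × 5 = 2.6 points, 0.529 × 7.07 = 3.7 points, or 0.529 × 10 = 5.3 points.

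**Step 6: the SD of 5 against eligibility.** The synopsis bases the halved range on enrolling patients with T-scores below 54, with low scores meaning more fatigue. The synopsis eligibility criterion is a score of 45 or more, and sections 4.1.1 and 5.1.1 also use 45. The restriction that produces SD 5 is not the one that selects patients.

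**The case against.** The strongest reply is that 86% and 81% may be correct for inputs that were not printed. The range restriction acts on scores at entry. Nothing restricts week-4 scores, and the synopsis itself gives 10 as the unrestricted SD. As step 3 shows, a week-4 SD of 10 with correlation 0.5 returns both figures with the stated test, two-tailed alpha and full sample. This stands to a degree: one cannot say that only an implausible correlation would produce the stated figures, since that holds only if the SD is the same at both visits. It does not rescue the text, because those inputs appear nowhere and are incompatible with 5/5 as the paired effect size.

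Other routes fit too. A one-sided, two-group normal formula with 15 and 20 per arm gives 86.3% and 81.2%. Leftover two-group wording in sections 8.2.2 and 8.5 might lead a reader to infer that this is the source. The documents do not say so, and several routes match equally well, so the origin stays open.

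The second reply is that nothing depends on these figures. The sample size rests on practical grounds and p-values are hypothesis-generating. That stands, and it limits the consequence. It does not make a printed power figure correct.

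**Conclusion.** The two power figures are wrong as written. The stated inputs give 99.96% and 99.85%, which is 14 and 19 percentage points above the stated 86% and 81%. That conclusion assumes only what the plan prints: paired t-test, effect sizes 1 and 0.8 in SDs of change, 30 and 40 pairs, two-sided 0.05.

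A reader might infer that the trial really has over 99% power, or more than it needs. The documents do not support that. SD 5 is not shown to be the SD of change, and the restriction behind it does not match eligibility. A reader might equally infer that 30 patients are too few; that is not supported either. Over an assumed SD of change from 5 to 10, power for a 5-point change with 30 patients runs from 99.96% down to 75.4%, so it can lie on either side of the stated 86%. The direction of the error for the real trial is unknown.

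This should be fixed, because the only completed power statement cannot be interpreted. It does not call the design or the planned enrolment of 30 into question.

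**What to change.** In the synopsis, delete the 86% and 81% figures. In section 8.5, delete the unfinished riociguat-versus-placebo power text. Put in both places: *30 evaluable participants give 80% power (two-sided 0.05 paired t-test) to detect a mean change of 0.53 SD of the change score (40 participants: 0.45 SD).*

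State the assumed SD of change and its basis, so that the T-score equivalent can be read; step 5 gives examples for 30 participants. If the basis is an SD of scores, give the SD at each visit and the correlation, and derive any range restriction from the eligibility criterion actually used.

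In section 8.1, align the remark about detecting only large differences with the new figure: 0.53 SD of change is below the 0.8 that the synopsis itself calls smaller.

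These are wording changes in the synopsis and sections 8.1 and 8.5, with no change in planned enrolment.

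A separate matter is the maximum sample size. The synopsis mentions asking the IRB for an option of 40, whereas section 8.5 is written to "allow for the inclusion of up to 100 subjects should 30 subjects be found to be an insufficient number for any reason". The two must be reconciled through the IRB, because that settles the permitted maximum enrolment and is more than a wording change.
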